1.0 Research Design

1.1 Purpose/Specific Aims

The overall purpose of this study is to assess the influence of e-cigarette advertisements (ads) and their high-impact ad features (flavor features, reduced exposure messages, and FDA-authorized claims) on perceptions and intentions of using e-cigarettes among young adults (ages 18-30). Using two randomized between-subject experiments in an online survey, the main goal of the first experiment is to examine the effect of viewing different flavor features (flavor name, product color that coincides with flavor name, flavor image, flavor sensation descriptor, and flavor choice claim) on self-reported e-cigarette use perceptions and use intentions. The main goal of the second experiment is to examine the effect of viewing different e-cigarette marketing claims suggesting harm reduction (reduced exposure claim, FDA-authorization claims) on self-reported e-cigarette use perceptions and use intentions.

A. Objectives

Objective 1: To assess if exposure to e-cigarette ads with flavor features and reduced harm claims will result in greater positive perceptions and increased e-cigarette use intentions than exposure to e-cigarette ads without these features.

B. Hypotheses / Research Question(s)

Hypothesis 1: Exposure to e-cigarette ads with flavor features and reduced harm claims will result in greater positive perceptions and increased e-cigarette use intentions than exposure to e-cigarette ads without these features.

Hypothesis 2: The positive effect of exposure to e-cigarette ads with flavor features on e-cigarette use intentions will be moderated by participants' tobacco-use status.

1.2 Research Significance

There has been a rise in e-cigarette use with nicotine among U.S. young adults in recent years.¹ Among those aged 19-30, past 12-month nicotine vaping increased from 13.7% in 2017 to 25.3% in 2023, while past 30-day nicotine vaping rose from 6.1% in 2017 to 18.7% in 2023.¹ This is concerning, given that e-cigarette use during young adulthood among those who are naïve to tobacco products can lead to nicotine addiction and may increase the risks of developing more harmful tobacco-use behaviors that can lead to respiratory diseases, cardiovascular diseases, and cancer later in life.^{2,3} On the other hand, young adults who smoke cigarettes may benefit from using e-cigarettes to quit smoking, as switching from cigarettes to e-cigarettes could reduce their exposure to harmful chemicals before they become vulnerable to the severe health effects of long-term cigarette smoking.⁴ E-cigarette marketing plays a key role in shaping the perceptions and use intentions of e-cigarette products among young adults of varying tobacco use behaviors.⁵⁻⁷ In our previous research, we found that exposure to flavor features, such as fruit flavor names, images, etc., is influential in increasing positive product perceptions and use interests.⁸⁻¹¹ This is unsurprising considering the availability of e-cigarettes in non-tobacco flavors is commonly cited as a key reason for e-cigarette initiation and use among young people.¹² However, it is unclear which specific flavor features (e.g., flavor names, colorful product packing that coincide with the product flavor [e.g., red for strawberry, green for apple], flavor images, flavor sensation claims) may be particularly appealing to young adults. It is also unknown which combinations of various flavor features appearing on an ad together are especially influential in changing perceptions and use intentions. In addition, various potential marketing claims related to reduced harm from e-cigarette use, including reduced exposure claim and FDA-authorized claims may also alter the perceptions and use intentions of the products. Additional research is needed to address significant gaps regarding which the impact of those features and claims used in e-cigarette ads among young adults with varying tobacco use behaviors and to inform regulatory decision-making. Regulatory decision-making related to e-cigarette flavor features on ads is important for helping to reduce the use of e-cigarettes with non-tobacco flavorings that may expose young people to aerosols containing compounds of respiratory toxicity.¹³

1.3 Research Design and Methods

To assess the impact of those features and claims, we will administer two separate randomized experiments through this online survey project where subjects will be assigned to one of six e-cigarette ad conditions (experiment 1) and one of the six e-cigarette ad conditions (experiment 2). The survey will include a series of questions about subjects' sociodemographic backgrounds, health

conditions, tobacco use history and dependence, and tobacco use environment. Static images of mock e-cigarette ads will be created based on publicized ads in brand company websites and emails.

A. Research Procedures

Young adult subjects will be recruited from online study panels administered by Qualtrics. Qualtrics will send out a brief description of the study for young adult recruitment (see Attachment A). Those who are interested in participating will first receive a screening survey (see Attachment B) to ensure eligibility. Those who are eligible will move on to the informed consent page (see Attachment C) and those who agree with the consent will proceed to complete the study survey (see Attachment D). In the survey, subjects will first answer a series of questions about demographics, health conditions, tobacco use history and dependence, and tobacco use environment. Afterward, for experiment 1, subjects will be randomly assigned to one of six conditions where they will be exposed to an e-cigarette ad either featuring an e-cigarette product that may or may not include high-impact flavor features. Condition 1 (control condition) will not include any high-impact flavor features and conditions 2-6 will include at least one high-impact flavor feature (flavor name, product color that coincides with flavor name, flavor sensation descriptor, and flavor choice claim). Attachment E includes stimuli for each experimental condition. Each ad will also include other ad features (e.g., nicotine warning label, generic marketing claim) to help increase ad authenticity. The conditions are:

- Condition 1: Black product with tobacco flavor name
- Condition 2: Black product with strawberry flavor name
- Condition 3: Colorful (strawberry color) product with strawberry flavor name
- Condition 4: Colorful (strawberry color) product with strawberry flavor name + strawberry image
- Condition 5: Colorful (strawberry color) product with strawberry flavor name + strawberry image + strawberry flavor sensation descriptor
- Condition 6: Colorful (strawberry color) product with strawberry flavor name + strawberry image + strawberry flavor sensation descriptor + flavor choice claim

We chose to assess strawberry as the product flavor in these ads because it is a commonly marketed and available e-cigarette flavor^{14,15} in the retail environment, and one of the most frequently mentioned e-cigarette flavors among users on social media sites.¹⁶⁻¹⁸ Strawberry has also been cited as one of the most appealing,^{14,19} and highly rated²⁰ e-cigarette flavors among users. It is therefore a flavor commonly used in e-cigarette research, including laboratory experiments, to assess user perceptions, use intentions, and use behaviors.^{14,15,20}

During the experiment, subjects will be required to view each ad for a minimum of 10 seconds and will then answer questions about their intentions and perceptions of using the e-cigarette products shown in each ad.

For experiment 2, subjects will be randomly assigned to one of six conditions where they will be exposed to an e-cigarette ad with or without reduced exposure claims, FDA-authorized claims, and scientific facts about FDA-authorized claims. Attachment E includes stimuli for each experimental condition.

- Condition 1: E-cigarette ad without any claims
- Condition 2: E-cigarette ad with reduced exposure claim
- Condition 3: E-cigarette ad with reduced exposure claim and FDA-authorized claim
- Condition 4: E-cigarette ad with reduced exposure claim, FDA-authorized claim, and scientific facts about FDA-authorization
- Condition 5: E-cigarette ad with FDA-authorized claim
- Condition 6: E-cigarette ad with FDA-authorized claim and scientific facts about FDA-authorization

During the experiment, subjects will be required to view each ad for a minimum of 10 seconds and will then answer questions about their intentions and perceptions of using the e-cigarette products shown in each ad.

After completing the survey questions, subjects will view debriefing messages about the harm of tobacco and e-cigarette use. The debriefing messages will also include information about how the tobacco industry targets young people with appealing advertisements and a list of e-cigarette and cigarette cessation resources for those who need quitting support.

B. Duration for Study and Each Subject

It will take subjects approximately 20 minutes to complete the entire survey.

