1.6 Study Variables

A. Independent Variables, Interventions, or Predictor Variables

The predictor variable will be subjects' conditions they are assigned to for the two experiments.

B. Dependent Variables or Outcome Measures

For both experiments, four groups of outcome measures will be used. See the Survey attachment for detailed measures

1. Ad appeal
2. E-cigarette use intentions
3. E-cigarette risk perceptions
4. E-cigarette outcome expectancies

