1.8 Data Collection

A. Primary Data Collection

- **Location:** The survey will be programmed online, via Qualtrics, an online survey platform.
- **Process of Data Collection:** Data collection will be managed by Qualtrics, and young adult subjects will be recruited from Qualtrics' existing study panels.
- **Timing and Frequency:** The survey will be a one-time occurrence estimated to take approximately 20 minutes.
- **Procedures for Audio/Visual Recording:** N/A
- **Study Instruments:** The survey is included with this application (see Attachment D). The study survey will assess tobacco-using history, perceptions about tobacco products and tobacco use, perceptions of e-cigarette ads with various features and claims, intentions perceptions of using the products in these ads, and subject demographics.
- **Ethnographic Studies, Interviews, Or Observation:** N/A
- **Subject Identifiers:** Data will be collected from young adult subjects online who are registered users of Qualtrics survey panels. Qualtrics takes extensive measures to ensure that all registered members' privacy and personal information are treated confidentially and kept secure. For this study, all data will be de-identified and anonymous to the PI and no personal information will be released to the PI. We will set up the Qualtrics survey in a way to not collect subjects' PI addresses using the Anonymous Response features, in order to collect completely anonymous survey responses. At the beginning of the survey, Qualtrics will generate a random Subject ID.

B. Secondary Data Collection

- **Type of Records:** N/A
- **Location:** N/A
- **Inclusion/Exclusion:** N/A
- **Data Abstraction Form(s):** N/A

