6.0 Data Management Plan

6.1 Data Analysis

We will use linear regressions to assess the associations between experimental conditions and various outcomes described above. We will add the interaction terms to the regression models to test the interactive effects of tobacco-use status and the experimental effect. We will also provide estimates of participant characteristics and assess their even distributions across conditions.

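### Experiment 2 appears to follow Experiment 1 in the same people and session, and no prespecified term examines whether the first ad alters the claim effects

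*Protocol*

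**What the plan says.** Protocol section 1.3 states that "we will administer two separate randomized experiments through this online survey project where subjects will be assigned to one of six e-cigarette ad conditions" in Experiment 1, and also to one of six in Experiment 2, so each person contributes to both. Section 1.3 A gives the sequence. Background questions come first; then "Afterward, for experiment 1, subjects will be randomly assigned to one of six conditions"; the Experiment 1 ad and its questions follow. The text then turns to the second experiment: "For experiment 2, subjects will be randomly assigned to one of six conditions where they will be exposed to an e-cigarette ad", with its own questions. Only after that comes the debrief: "After completing the survey questions, subjects will view debriefing messages about the harm of tobacco and e-cigarette use".

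Section 1.8 A makes this a single sitting: "The survey will be a one-time occurrence estimated to take approximately 20 minutes". Section 1.6 B assigns the same outcomes to each part: "For both experiments, four groups of outcome measures will be used" (ad appeal, use intentions, risk perceptions, outcome expectancies).

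In Experiment 1, condition 1 carries a tobacco flavor name and conditions 2 to 6 all carry a strawberry name.

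On analysis, section 6.1 says "We will use linear regressions to assess the associations between experimental conditions and various outcomes described above", and the SAP repeats it. The only interaction that either names is with tobacco-use status. Neither mentions Experiment 1 condition in the Experiment 2 model.

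**The concern.** Section 1.1 gives the goal of Experiment 2 as the effect of viewing harm-reduction claims, and Hypothesis 1 compares ads with such claims to ads without them. On the sequence described, no subject gives a first response to a claims ad. Everyone has just seen another study ad and answered the same kinds of questions, and for most that ad was built to make a strawberry product attractive.

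The protocol itself makes some carry-over plausible. Section 1.2 reports from the team's earlier work that flavor features raise positive perceptions and use interest, and section 1.4 gives related findings. These are the kinds of outcome that Experiment 2 measures next.

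What is at stake is the meaning of the Experiment 2 result. If a recent flavor ad weakens or strengthens the response to a claim, the reported effect averages over two kinds of viewer, weighted heavily to those who saw strawberry. Without a prespecified look at this, a small claim effect could not readily be told from one diluted by the earlier ad.

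**Working it through.** **Inputs from the documents**
- Total 3,000 (sections 1.5 and 4.3), with 500 per group in six conditions (section 1.5).
- One of six Experiment 1 ads is tobacco-flavored and five are strawberry (section 1.3 A).

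**Assumptions, because the documents give no figures**
- Equal allocation, which 500 per group implies, and two independent randomizations.
- Outcome SD of 1, two-sided 5% test, 80% power, so the multiplier is 1.960 + 0.842 = 2.80.
- An illustrative claim effect of 0.20 SD after the tobacco ad.

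**1. The plan's own figure.** 6 × 500 = 3,000, which matches. The statement that power is sufficient cannot be reproduced, because no alpha, power, SD or numeric effect size is given.

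**2. Who enters Experiment 2.**
- After a strawberry ad: 3,000 × 5/6 = 2,500, or about 417 of the 500 in each Experiment 2 arm.
- After the tobacco-flavor ad: 3,000 × 1/6 = 500, or about 83 per arm (3,000/36 = 83.3).
- After no study ad: 0, since all six Experiment 1 conditions show one.

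**3. Additive carry-over.** If the strawberry ad shifts every later answer by the same amount, the shift is spread equally over the Experiment 2 arms and drops out of their differences. A simulation of 4,000 trials, with a 0.3 SD shift after strawberry and a true claim effect of 0.200 SD, gave a mean estimate of 0.201 SD.

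**4. Carry-over that changes the claim effect.** The expected estimate is

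reported effect = (5 × effect after strawberry + effect after tobacco ad) / 6.

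Power is for one claim-versus-control contrast at 500 per arm.

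| Effect after tobacco ad | Effect after strawberry | Reported effect (SD) | Power |
|---|---|---|---|
| 0.20 | 0.20 (no change) | 0.200 | 88.5% |
| 0.20 | 0.15 | (0.75 + 0.20)/6 = 0.158 | 71% |
| 0.20 | 0.10 | (0.50 + 0.20)/6 = 0.117 | 45% |
| 0.20 | 0.00 | (0.00 + 0.20)/6 = 0.033 | 8% |
| 0.20 | 0.30 (amplified) | (1.50 + 0.20)/6 = 0.283 | not computed |

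The same simulation, with the effect halved after strawberry, also gave 0.117 SD.

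**5. What the data could show about this.** For one claim-versus-control contrast:
- All subjects, 500 per arm: SE = √(2/500) = 0.063; detectable effect 2.80 × 0.063 = 0.177 SD.
- After strawberry, 417 per arm: SE = √(2/416.7) = 0.069.
- After the tobacco ad, 83 per arm: SE = √(2/83.3) = 0.155; detectable effect 0.434 SD.
- Difference in claim effect between the two strata: SE = √(2/83.3 + 2/416.7) = √0.0288 = 0.170; detectable difference 2.80 × 0.170 = 0.475 SD.

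**6. If the order of the experiments were randomized 1:1.** About 250 per arm would have each experiment first: SE = √(2/250) = 0.089, detectable effect 0.25 SD. Experiment 2 measurements taken after a strawberry ad would fall from 2,500 to 1,250.

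**The case against.** The strongest reply is that the randomized comparison is sound, and this stands. Under independent randomization every Experiment 2 arm has the same mix of prior ads on average. A reader might infer that the no-claim arm is a contaminated control, or that Experiment 2 is confounded by Experiment 1. The documents support neither inference. Harm requires that the earlier ad modify the claim effect. The findings cited in sections 1.2 and 1.4 concern the influence of flavor features themselves, and nothing in the documents shows that they interact with claims. The modification could also go in either direction, as the last row of the table shows.

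Four further points stand:
- Fixed order is inferred. Section 1.3 A has a time word before Experiment 1 but none before Experiment 2, and Attachment D might contain a filler task or a randomized order.
- A reader might think that the carry-over could never be examined. It can: Experiment 1 condition is a randomized study variable (section 1.6 A) and should be in the data. What is missing is a prespecified term, and power.
- A reader might say that any positive result applies only after a flavor-feature ad. About one subject in six will have seen the tobacco-flavor control instead. Nor is that group unexposed, because it too saw an e-cigarette ad and answered the questions.
- The outcome questions refer to the products in the ad shown, which may limit transfer. Section 4.7 A notes that young adults meet such ads in daily life, so an effect after prior exposure is interpretable, although exposure earlier in the same survey is more immediate.

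These points narrow the concern but do not remove it. The sequence described still determines what Experiment 2 estimates, and the plan neither says so nor provides a look at it.

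**Conclusion.** The point holds as a matter of interpretation and prespecification, not of bias in the randomized contrast. On the natural reading of section 1.3 A, Experiment 2 estimates the effect of claims in people who have just seen another e-cigarette ad, a strawberry one for about 2,500 of 3,000. If the claim effect does not depend on that ad, nothing is lost. If it does, the reported effect is the 5:1 average above: for an assumed 0.20 SD after the tobacco ad and an effect weakened by 25% to 100% after strawberry, 0.158 down to 0.033 SD. The size of any such change is unknown, and these values are illustrations.

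The conclusion rests on equal allocation, independent randomizations and the inferred order. If Attachment D already randomizes the order, the remaining need is to state that in the protocol and put order in the models. Experiment 1, if it comes first, is unaffected.

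**What to change.** **Section 1.3 A.** State the order of the two experiments and any break between them. Randomize Experiment 2 evenly within each Experiment 1 arm.

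**Section 6.1 and the SAP.** Include Experiment 1 condition as a covariate in every Experiment 2 model. Prespecify an exploratory interaction of claim condition with prior ad type (strawberry, arms 2 to 6, versus tobacco flavor, arm 1), and report the claim effects with confidence intervals in both strata.

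**Reporting.** Word the Experiment 2 conclusion as the effect of claims in people who have just seen another e-cigarette ad and answered the same questions.

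**Cost.** A survey-flow setting and a few lines of text, with no added subjects. The limits should be stated too. The interaction test reaches 80% power only for differences of about 0.475 SD, so a non-significant result is not evidence of no carry-over. It also cannot detect anchoring on earlier answers, which is common to both strata.

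**An option to weigh, not the lead change.** Randomizing the order of the experiments would give a true first-position estimate for Experiment 2. It would also open Experiment 1 to carry-over and leave about 250 per arm for its first-position estimates (detectable effect 0.25 instead of 0.177 SD), or about 83 per arm within each of the three tobacco-use groups (250/3). Hypothesis 2 concerns flavor features only and depends on those groups, so the investigators may reasonably keep the flavor experiment first.

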1.4 Preliminary Data

This study is informed by preliminary data from several of our previous projects. For instance, our previous online heatmap experiment study,⁸ eye tracking studies,^{9,10} and in-depth interviews¹¹ all provide information about the most impactful e-cigarette marketing features in changing perceptions and use interests among young adults of various tobacco use behaviors. In our online heatmap experiment, we found that noticing fruit flavors and fruit images in e-cigarette ads was associated with e-cigarette product appeal and switching interest among young adult dual-users of e-cigarettes and cigarettes.⁸ Noticing price promotions was also associated with e-cigarette product appeal, but no other features were influential in increasing participants' interest in completely switching to e-cigarettes.⁸ In our eye-tracking study assessing cartridge-based e-cigarette product features in print ads, we found that overall, longer dwell time for multiple flavor choice descriptions (choice of fruit, menthol, tobacco flavors) was positively associated with e-cigarette appeal, and a shorter entry time for fruit flavor descriptions was associated with positive e-cigarette use expectancies.⁹ Similarly, in our eye-tracking study assessing disposable e-cigarette product features in social media marketing, attention to fruit/candy descriptors (names and promotional claims for fruit and candy flavors) generated product use interest among young adults who smoke.¹⁰ Our interviews that followed the eye-tracking study for cartridge-based e-cigarette products revealed that young adults who do not use tobacco and those who smoke cigarettes generally noticed fruit and multiple flavors in the ads, which were seen as appealing and were reported to generate product use interest because of bright colors, sensory appeal, and a variety of flavor options.¹¹ Based on the findings from these studies, it is important to further assess the influence of flavor features in e-cigarette ads to understand which flavor features, or which combination of flavor features together, are most impactful in changing perceptions and use interests.

1.5 Sample Size Justification

There will be 3,000 subjects enrolled in the study. Our previous studies using a similar study design examining the influence of e-cigarette marketing features used sample sizes of approximately 3,000 to obtain sufficient power for detecting differences in product perceptions and use interest with small to moderate effect sizes. Other studies have shown that 500 subjects per group (6 randomizing conditions) will provide sufficient power to detect differences in perceptions and use intentions after viewing varying ad features as well as the moderating effect of tobacco-use status on those associations.

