4.0 Subject Considerations

4.1 Subject Selection and Enrollment Considerations

A. Method to Identify Potential Subjects

Subjects will be registered Qualtrics study panel members. Potential subjects will initially review a brief description of the study (see Attachment A), and those who are interested in participating will proceed to the eligibility screening questions assessing their age and tobacco use history (see Attachment B). If eligible, they will then be directed to the online consent form (see Attachment C).

B. Recruitment Details

In Spring 2025, subjects will be recruited via Qualtrics' online study panels. Potential subjects who see and choose to complete our task (i.e., study) will complete it using Qualtrics' survey platform. Recruitment is anticipated to take approximately three weeks.

C. Subject Screening

▪ Inclusion Criteria

Three groups of young adult subjects (ages 18-30) will be included in the study. The first group is those who are exclusive cigarette smokers (n=1000), defined as those who have smoked at least 100 cigarettes in their lifetime and have smoked at least one cigarette in the past 30 days but have not used e-cigarettes in the past 30 days. The second group is those who are dual users of cigarettes and e-cigarettes (n=1000). Those in this group have smoked more than 100 cigarettes in their lifetime and have smoked a cigarette and also used an e-cigarette in the past 30 days. The third group is those who are non-tobacco users (n=1000), defined as those who have never used any tobacco product before or have never "regularly" used tobacco products before and are currently not using any tobacco products (in the past 30 days).

▪ Exclusion Criteria

Any subjects not meeting the inclusion criteria described in 4.1.C will be excluded from the study. Individuals will be further excluded if they do not provide consent to participate in the study.

D. Privacy Protections

Our survey will be publicized via Qualtrics (see Attachment D) to their registered study panel members. The screening questions (see Attachment B) pertain solely to demographics and tobacco use history and do not request any personally identifiable information. The PI will not receive the responses to the screening questions from Qualtrics if the subjects do not agree with the consent form or do not complete the survey.

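### Does the unquantified power statement for moderation, with ten interaction terms and no named test, leave Hypothesis 2 without a sound analysis?

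*Protocol*

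**What the plan says.** Hypothesis 2 (Protocol 1.1 B) is a single statement: "The positive effect of exposure to e-cigarette ads with flavor features on e-cigarette use intentions will be moderated by" tobacco-use status. Section 1.5 sets the total: "There will be 3,000 subjects enrolled in the study". It then makes the power claim: "Other studies have shown that 500 subjects per group (6 randomizing conditions) will provide sufficient power" for differences in perceptions and use intentions "after viewing varying ad features as well as the moderating effect of tobacco-use status on those associations". It gives no alpha, SD, power value or size of moderation.

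The predictor is the set of "conditions they are assigned to for the two experiments" (section 1.6), and in each experiment "subjects will be randomly assigned to one of six conditions" (section 1.3). Section 4.1 C recruits three tobacco-use groups of equal size, the last described as follows: "The third group is those who are non-tobacco users (n=1000". The moderation analysis is one sentence, the same in Protocol 6.1 and in the SAP: "We will add the interaction terms to the regression models to test the interactive effects of tobacco-use status and the experimental effect". Neither document gives a coding, a reference group, a joint test or a significance level.

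**The concern.** Moderation is one of only two stated hypotheses. Under reference coding, each interaction term compares one ad with Condition 1 between two tobacco-use groups. Hypothesis 2 is about flavor-feature ads across all three groups, and no single term estimates that. If an analyst declared the hypothesis supported whenever any term reached p<0.05, the false-positive rate would be far above 5%, and the result would depend on which group served as reference.

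Section 1.5 also covers a condition difference and its moderation with one claim of sufficient power, although the same sample detects a much smaller difference of the first kind than of the second. A reader cannot check the moderation part of that claim.

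**Working it through.** **Inputs.** From the Protocol: 3,000 subjects and 500 per condition (1.5), six conditions (1.3), three groups of 1,000 (4.1 C). Assumed here, because the documents do not give them: two-sided alpha 0.05, residual SD of 1, equal cells.

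**The plan's own figures.** 6 x 500 = 3 x 1,000 = 3,000, so the totals agree. Each condition-by-status cell holds 3,000/18 = 166.7. The power claim cannot be reproduced, since no effect size, alpha or power value is stated.

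**Number of terms.** (6 - 1) x (3 - 1) = 10 per outcome in each experiment.

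**False positives if the terms are read singly.** Under reference coding, two terms have correlation 0.5 if they share a condition or a status group, and 0.25 otherwise. Simulating the chance that the largest of ten |Z| exceeds 1.96 gives 31.0%. A check with unequal cells from simple randomization gives 31.4%. Effect coding gives 36.3%. Independent terms would give 1 - 0.95^10 = 40.1%. A joint 10-df F test holds 5%, and so does a 2-df test of pooled Conditions 2-6 against Condition 1 by status.

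**Detectable sizes at 80% power.**
- One condition against control, all groups together: 2.802 x sqrt(2/500) = 0.18 SD.
- Moderation with equal effects of all flavor ads and one group differing from the other two: noncentrality = 166.7 x d² x (2/3) x (5/6) = 92.6 d². The pooled 2-df test needs 9.64, so d = sqrt(9.64/92.6) = 0.32 SD. The 10-df test needs 16.29, so d = sqrt(16.29/92.6) = 0.42 SD.

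**Does one joint test dominate?** Power at d = 0.3 SD, with one tobacco-use group differing from the other two. Noncentrality is 166.7 x 0.09 x (2/3) x S = 10 x S, where S is the sum of squares of the condition pattern about its mean. The pooled and trend tests keep only the part of S that lies along their own contrast.

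| Pattern of the effect over conditions | S | Pooled 2-df | Joint 10-df | Trend 2-df |
|---|---|---|---|---|
| Equal in Conditions 2-6 | 5/6 | 74% | 45% | not computed |
| Steady growth from Condition 1 to 6 | 0.70 | 32% | 38% | 65% |
| Conditions 4-6 only | 1.50 | 32% | 76% | 87% |

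In the last two rows the pooled test keeps a noncentrality of 3.0, out of 7.0 and 15.0 respectively. The trend test keeps all 7.0 in the second row and 11.6 of 15.0 in the third. The order of the tests reverses with the pattern.

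**The case for a change.** The best case for a change is that the choice of test stays open until the data are in, on one of two hypotheses, and that a few sentences would close it with the same model and no extra subjects. It does not depend on showing that power is low. The arithmetic behind it is right: ten terms, about 31% if they are read singly, and a detectable moderation of 0.32 to 0.42 SD against 0.18 SD for a single condition difference.

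It stands as a remark on missing detail. It does not stand as an error in the method:

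- The 31% belongs to a decision rule that neither document states. It also needs an alpha and a coding that the documents do not give. Adding a set of terms in order to test the interactive effects is the ordinary description of a joint interaction test, and a statistician carrying out the SAP would report one.
- The pooled contrast is not the only reading of Hypothesis 2. Sections 1.2 and 1.4 ask which features, and which combinations, matter most. Conditions 2-6 add features cumulatively, and averaging them discards that structure.
- A joint 10-df test also gives the same answer whichever group is the reference, and it does not assume equal effects.
- Writing an alpha, a cell size and a detectable difference into section 1.5 would record more detail, but it would correct no figure that the plan states.

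**Conclusion.** No change follows. The plan is brief about moderation, and section 1.5 supports its claim only by reference to other studies. The gap is one that analysts fill sensibly: a joint condition-by-status test for use intentions in Experiment 1, with the ten single terms read as description. That keeps the error rate at 5%. The figure of 31% (36% to 40% under effect coding or independence) applies only if the terms are read one at a time at an assumed two-sided 0.05.

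Inadequate power is not shown. With about 167 per cell and unit SD, 80% power is reached at 0.32 SD (pooled) or 0.42 SD (10-df) when all flavor ads act equally and one group differs. The plan states no moderation size to set against these. Which joint test is strongest depends on an effect pattern that nobody yet knows, so requiring the pooled contrast would exchange one risk for another. All of this takes use intentions as a single score; the Survey attachment that would confirm it is not among the documents.
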